5.3.2. Dose Interruption and Modification Due to Toxicity

Study drug may be interrupted or reduced as described in [Table 7](#) at the discretion of the Investigator at any time due to AEs and according to the guidelines described in [Table 8](#), [Table 9](#), and [Table 10](#). Whenever possible, dose reductions must be prospectively discussed with the Sponsor. If study drug is interrupted and then study drug is restarted, the patient should remain on their original cycle schedule.

If any patient requires a dose lower than 50 mg QD or if a patient has had their dose reduced and has disease progression confirmed by the independent radiologic reviewer, the patient must be discontinued from study drug, the End-of-Treatment (EOT) Visit and Safety Follow up Visit must be conducted, and the patient must be followed for overall survival.

Table 7: Dose Reduction Steps for Study Drug

Starting Dose of Study Drug	1 ST Dose Reduction	2 ND Dose Reduction
150 mg QD	100 mg QD	50 mg QD

Following disease progression by modified RECIST, patients who dose escalate to 150 mg BID and have toxicity must be dose reduced according to the steps outlined in [Table 8](#).

Table 8: Dose Reduction Steps for Patients Who Progressed and Dose Escalated to 150 mg BID

Starting Dose of Study Drug	1 ST Dose Reduction	2 ND Dose Reduction
150 mg BID	100 mg BID	150 mg QD

If the AE returns to Grade 1 or baseline, the patient may be re-escalated. Efforts must be made to re-escalate the patient to the dose level at which the AE occurred. If the dose level is reduced to the 1st dose reduction level and the AE returns to Grade 1 or baseline, the patient may be re-started at the starting dose level. If a patient has two sequential dose reductions and the AE returns to Grade 1 or baseline at the 2nd dose reduction level, the patient may be re-started at the 1st dose reduction level and must remain at this dose level for 1 cycle without interruption before escalating to the starting dose level.

If the AE leading to dose modification does not return to Grade 1 or baseline within 1 cycle (28 days), then the study drug must be discontinued, unless the event is considered not clinically significant by the Investigator, in which case the possibility of restarting the patient at a reduced dose level may be made after consultation with the Sponsor.

Table 9: Dose Modifications for Dermatologic Toxicities and Arthralgia/Myalgia

Toxicity Grade	Dose Modification Guide

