Grade 1	Institute support measures and continue the study drug at the current dose
Grade 2	
Institute support measures and continue the study drug at the current dose
 
If no improvement within 7 days, then interrupt the study drug
 
 • If the event returns to Grade 1 or baseline within 7 days, resume the study drug at the same dose level • If the event returns to Grade 1 or baseline after 7 days, resume the study drug at a reduced dose level 
If this is a recurrence, after event returns to Grade 1 or baseline, resume the study drug at a reduced dose level regardless of time to improvement
 
If after a dose reduction the event is maintained at Grade 1 or baseline for at least 1 cycle (28 days) of dosing, consider re-escalating the study drug by 1 dose level

Grade 3	
Institute support measures
 
Interrupt study drug for at least 7 days or until the event returns to Grade 1 or baseline (maximum 28 days)
 
 • Resume study drug at a reduced dose level 
If after a dose reduction the event is maintained at Grade 1 or baseline for at least 1 cycle (28 days) of dosing, consider re-escalating the study drug by 1 dose level

Grade 4	Discontinue study drug unless the event is not considered life-threatening. Patients may continue study drug with non-life threatening events upon discussion with the Sponsor.
Any Grade	
Stevens-Johnson Syndrome:
 
If a patient experiences Stevens-Johnson syndrome (SJS), study drug must be permanently discontinued. The patient should be immediately referred to a hospital for clinical evaluation and supportive care/management per institutional guidelines. Re-administration of study drug is not allowed due to the risk of recurrent SJS. Caution for recurrence of SJS with other similar agents (TKIs for GIST) is advised, as the one patient who has been diagnosed with SJS while being treated with DCC-2618 had a similar reaction while being treated with regorafenib prior to DCC-2618.

Table 10: Dose Modifications and Management of Hypertension

Toxicity Grade	Management Guideline*
Grade 1 Prehypertension (systolic BP 120 - 139 mm Hg or diastolic BP 80 - 89 mm Hg)	Continue BP monitoring Continue the study drug at the current dose level

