Grade 2 Systolic BP 140 - 159 mm Hg or diastolic BP 90 - 99 mm Hg Or Symptomatic increase by >20 mm Hg (diastolic) or to >140/90 mm Hg if previously within normal limits	Treat BP to achieve diastolic BP ≤ 90 mmHg and or systolic BP ≤ 140 mmHg 
 • If BP was previously within normal limits, start antihypertensive monotherapy • If patient is already on antihypertensive medication, titrate dose up Continue the study drug at the current dose level Hold study drug if symptomatic increase by 20 mmHg (diastolic BP) until symptoms resolve and diastolic BP ≤ 90 mmHg On resuming study drug, continue at the same dose level
Grade 3 Systolic BP ≥ 160 mm Hg or diastolic BP ≥ 100 mm Hg) Or More than 1 drug or more intensive therapy than previously indicated	Treat to achieve diastolic BP ≤ 90 mmHg and or systolic BP ≤ 140 mmHg 
 • Start antihypertensive medication and/or • Increase current antihypertensive medication and/or • Add additional antihypertensive medication If symptomatic, hold study drug until diastolic BP ≤ 90 mmHg and/or systolic BP ≤ 140 mmHg, and symptoms resolve On resuming study drug, continue at the same dose level If BP is not controlled with addition of a new or more intensive therapy, reduce the study drug by 1 dose level If Grade 3 hypertension recurs despite study drug dose reduction and antihypertensive therapy, reduce the study drug by 1 additional dose level
Grade 4 Life-threatening consequences (eg, malignant hypertension, transient or permanent neurologic deficit, hypertensive crisis)	Treat BP per institutional guidelines Discontinue study drug

BP=blood pressure

*If BP remains controlled for at least 1 full cycle (28 days), study drug dose re-escalation is permitted at the Investigator's discretion.

Table 11: Dose Modifications for Treatment Related Adverse Events Other than Dermatologic Toxicities, Arthralgia/Myalgia, and Hypertension

Toxicity Grade	Management Guideline ¹
Any Grade 3 or 4	Interrupt study drug dosing until event has resolved to Grade 1 or baseline Once the AE returns to Grade 1 or baseline, reduce study drug by 1 dose level If a patient tolerates the reduced dose without recurrence of the event for at least one cycle, consider re-escalating the dose of study drug to the prior dose level

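### Protocol Table 9 lets a Grade 3 skin or joint event restart drug after 7 days without recovery, because its two hold conditions are joined by *or*

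*Protocol*

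**What the plan says.** Table 9 (Protocol Section 5.3.2) governs dermatologic toxicities and arthralgia/myalgia. Its Grade 3 row reads "Interrupt study drug for at least 7 days or until the event returns to Grade 1 or baseline (maximum 28 days". The bullet below it has study drug resumed at a reduced dose level and names no grade that must be reached first.

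The Grade 2 row of the same table starts with drug continuing at the current dose, then "If no improvement within 7 days, then interrupt the study drug". After an interruption there are three restart paths:
- Recovery to Grade 1 or baseline within 7 days leads to the same dose.
- Slower recovery: "If the event returns to Grade 1 or baseline after 7 days, resume the study drug at a reduced dose level".
- Recurrence: "If this is a recurrence, after event returns to Grade 1 or baseline, resume the study drug at a reduced dose level", however long improvement takes.

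Table 11 covers treatment-related events other than skin, joint/muscle and hypertension. For any Grade 3 or 4 event it says "Interrupt study drug dosing until event has resolved to Grade 1 or baseline", and then "Once the AE returns to Grade 1 or baseline, reduce study drug by 1 dose level".

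Two time limits also apply. Section 5.3 caps any interruption at one 28-day cycle. Section 5.3.2 addresses non-recovery: "If the AE leading to dose modification does not return to Grade 1 or baseline within 1 cycle (28 days"), treatment has to stop. It allows one exception, which needs Sponsor consultation: "unless the event is considered not clinically significant by the Investigator, in which case the possibility of restarting the patient at a reduced dose level".

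**The concern.** With *or* between the two conditions, meeting either one ends the hold. A site applying the row as written could re-dose on day 7 a patient whose Grade 3 skin or joint toxicity has not improved. The same wording lets a patient who recovers on day 2 restart on day 2, so the stated 7-day minimum has no force. The more severe grade then has a looser restart condition than Grade 2 in the same table.

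Skin is a known concern for this drug. All three adverse events of special interest in Section 7.9 are skin lesions, Table 9 itself describes a case of Stevens-Johnson syndrome on DCC-2618, and the dog study in Section 1.3.1.3 reports skin findings among the observations that led to early sacrifice. About 35 centers will apply the row, and they could read it differently. What is at stake is patient safety and consistent dosing; the efficacy analyses do not depend on it.

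**Working it through.** The plan gives no figure to reproduce. The check is a side-by-side reading of the rules, followed by simple date arithmetic.

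**Step 1. Restart-after-interruption paths in Tables 9 and 11, laboratory rows excluded**

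| Path | Needed before restart | Restart dose |
|---|---|---|
| Table 9, Grade 2, recovery within 7 days | Grade 1 or baseline | Same |
| Table 9, Grade 2, recovery after 7 days | Grade 1 or baseline | Reduced |
| Table 9, Grade 2, recurrence | Grade 1 or baseline | Reduced |
| Table 11, any Grade 3 or 4 | Grade 1 or baseline | Reduced by one level |
| Table 9, Grade 3 | 7 days elapsed *or* Grade 1 or baseline | Reduced |

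Four of the five require recovery. The Table 9 Grade 3 row is the only one that does not.

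**Step 2. Does other text close the gap?** The Section 5.3 cap limits how long a hold may last. The Section 5.3.2 rule acts when 28 days have passed without recovery. Neither makes recovery a condition of a restart before day 28.

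**Step 3. Effect of the connector on timing.** Let R be the day of the hold on which the event reaches Grade 1 or baseline, with R no later than 28.

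- As written (*or*): earliest restart = min(7, R).
- With *and*: earliest restart = max(7, R).
- Difference = |R − 7| days.

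| Case | *or* | *and* | Added hold |
|---|---|---|---|
| Recovery on day 2 | day 2 | day 7 | 7 − 2 = 5 days |
| Still Grade 3 on day 7, recovery on day 28 | day 7 | day 28 | 28 − 7 = 21 days |
| Not recovered by day 28 | day 7 | Section 5.3.2 rule applies | 21 days, then that rule |

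**Step 4. Is the literal reading workable?** A patient restarted while still Grade 3 meets the same row's trigger to interrupt again. The rule then loops, which suggests the literal *or* was not intended. It does not tell a site which reading to follow.

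**The case against.** The strongest reply is that this is loose drafting with little practical risk.

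- **Intent.** The loop in Step 4, and the 28-day rule's treatment of non-recovery as grounds for discontinuation, both point to recovery as the intended condition. This is probably right, and it supports correcting the text.
- **Oversight.** Restart is always at a reduced dose, and the Investigator may hold longer. Section 5.3.2 wants dose reductions discussed with the Sponsor beforehand where possible. Section 6.11.8, within its laboratory text, asks for every effort to discuss dosing changes first, or failing that to inform the Sponsor the same day. These lower the chance of an unreviewed day-7 restart. They do not make recovery a condition of it.
- **Comparators.** Table 11 excludes skin and joint events by its title, so the two tables are parallel rules of unequal strictness and do not conflict over one event. Some other rows do not use the Grade 1 standard either: Table 9's Grade 4 row allows continuation in non-life-threatening cases after Sponsor discussion, Table 11's laboratory rows can allow drug at Grade 3, and Table 10 uses blood-pressure targets and symptoms. This narrows the 4-of-5 count to the paths listed. The comparison with Table 9's own Grade 2 row is unaffected.
- **Size and remedy.** The 21 and 5 days describe hypothetical patients; nothing here estimates how often Grade 3 skin or joint events occur or persist past day 7. *And* would also keep a patient improved to Grade 2 by day 7 off drug, although the Grade 2 row initially doses through Grade 2 events. Both points stand and are costs to weigh.

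**Conclusion.** The concern holds. As written, the Table 9 Grade 3 row permits a reduced-dose restart after 7 days with the event still Grade 3, and no other text prevents it before day 28. It is the one non-laboratory restart path of five in Tables 9 and 11 without a recovery requirement. The conclusion rests on reading *or* literally; if sites already read it as *and*, practice would not change and only the wording needs repair. The clear anomaly is restart while still Grade 3. Table 9 does not forbid all dosing before recovery, since its Grade 2 row continues drug at first. This is a minor safety correction that should be made, with no bearing on PFS, ORR or any other efficacy analysis.

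**What to change.** In the Table 9 Grade 3 row, replace *or* with *and*, so that the hold lasts at least 7 days and continues until Grade 1 or baseline, up to 28 days, with restart at a reduced dose level only then. Add a cross-reference sending events unrecovered at day 28 to the existing Section 5.3.2 rule: discontinue, unless the Investigator judges the event not clinically significant, in which case a reduced-dose restart may be considered after Sponsor consultation.

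If the Sponsor does not want a 7-day floor, the row can simply require a hold until recovery. If restart at Grade 2 was intended, the row should say so.

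The change is one connector and one cross-reference, by amendment or clarification letter, with no new assessments. Under *and*, patients unrecovered at day 7, including those improved only to Grade 2, could be off drug for up to 21 more days, and those who recover sooner would wait until day 7.

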5.4. Packaging and Labeling

DCC-2618 will be supplied by the Sponsor as formulated drug in tablets for oral administration containing 50 mg of study drug in 30-count high-density polyethylene (HDPE) bottles with child resistant caps.

Placebo tablets of matching size, shape, and color, will be supplied by the Sponsor in matching 30-count HDPE bottles with child resistant caps.

Study drug labeling will be in accordance with applicable local and national regulations.

Study drug will be provided and replaced via the Interactive Response Technology (IRT). Study drug dispensation instructions will be provided in the Pharmacy Manual.

5.5. Storage Conditions

Study drug bottles must be stored tightly closed between 5°C/41°F and 25°C/77°F, away from sunlight and areas of high humidity (ie, near showers in bathrooms) and according to the instructions provided in the Pharmacy Manual. Excursions between 2°C/35.6°F and 27°C/80.6°F are allowed. While at the clinical site, the study drug must be stored in a secure, temperature-monitored area of limited access and only at the location(s) listed on the Form FDA 1572.

Instructions regarding the storage and handling of study drug after dispensation to patients will be provided to site in the Pharmacy Manual.

5.6. Study Drug Compliance

To ensure study drug compliance, the Investigator or designee must supervise all study drug dosing that occurs at the site. At each visit, site personnel must review that the patient is compliant with study drug dosing and remind the patient of study drug dosing requirements. Compliance must also be assessed by ongoing study drug count.

If a patient demonstrates continued noncompliance of study drug dosing despite educational efforts, the Investigator must contact the Sponsor to discuss discontinuation of the patient from the study.

5.7. Study Drug Accountability

Accountability for the study drug at the study site is the responsibility of the Investigator. The Investigator must ensure that the study drug is used only in accordance with this protocol. Where allowed, the Investigator may choose to assign drug accountability responsibilities to a pharmacist or other appropriate individual. Drug accountability records indicating the study drug's delivery date to the site, study drug inventory at the site, study drug dispensed to each patient, study drug returned by each patient, and study drug returned to the Sponsor or study drug destruction on site must be maintained by the clinical site. Accountability records must include dates, quantities, bottle numbers, and patient numbers. The Sponsor or its designee must review drug accountability at the site on an ongoing basis during monitoring visits. If any dispensing errors or discrepancies are discovered, the Sponsor must be notified immediately.

Patients must be instructed to return all unused, partially used, and used study drug bottles to the site at each visit. The study monitor must verify study drug records and inventory throughout the study.

5.8. Disposal, Return, or Retention of Unused Study Drug

Patients must be instructed to return all used, partially used, and full study drug bottles. The site staff or pharmacy personnel (as appropriate) must retain all materials returned by the patients until returned to Sponsor/designee or destroyed by the study site. If the study drug will be destroyed at the study site, the Investigator or designee, must ensure that the materials are destroyed in compliance with applicable environmental regulations, institutional policy, and any special instructions provided by the Sponsor. Destruction must be adequately documented.

5.9. Method of Assigning Patients to Treatment

Patients will be randomized in a 2:1 ratio to DCC-2618 150 mg or placebo. Randomization will be stratified by:

- Patients who have received 3 prior anticancer treatments versus patients who have received ≥ 4 prior anticancer treatments
 - It should be noted that enrollment for patients who have received ≥ 4 prior anticancer treatments will be limited to 40% of the overall sample size.
 - Prior anticancer treatments are only counted once and without regard to when the patient received treatment, unless they were given as combination treatments.
- ECOG=0 versus ECOG=1 or 2

The IRT will be used to assign study drug treatment. Detailed instructions for randomization will be provided separately.

5.10. Blinding and Unblinding

This is a double-blind study.

5.10.1. Blinding

The patients and all site personnel, including the Investigator, the site monitor, and the study team must be blinded, with the exception of the following:

- Any site personnel for whom this information is important to ensure the safety of the patient in the event of a life threatening medical emergency
- Any site personnel for whom this information is important to ensure the safety of the patient and their fetus in the event of a pregnancy
- Vendors responsible for pharmacovigilance and regulatory personnel at the Sponsor to satisfy serious adverse event (SAE) processing and reporting regulations
- Clinical Supply Chain
- Unblinded statistician and programmer preparing the final (production) randomization list and unblinded analyses for the independent data monitoring committee (IDMC)
- IDMC
- Vendors analyzing PK and biomarker samples
- Vendor conducting the population PK analysis
- IRT vendor

- The Investigator, patient, site personnel, site monitor and study team will become unblinded to a specific patient's treatment assignment, if the patient has disease progression based on independent radiologic review.

5.11. Unblinding

Instructions for unblinding through IRT will be provided in the Study Reference Manual.

Unblinding of the individual patient's study drug assignment by the Investigator must be limited to the following: medical emergencies in which knowledge of the patient's study drug is necessary for clinical management. In cases of medical emergencies, the Investigator must use their best judgment as to whether to unblind. If the Investigator deems it is not necessary to unblind immediately, the Investigator must first attempt to contact the Sponsor to discuss and agree to the need for unblinding. If the Investigator has tried but is unable to reach the Sponsor, the Investigator must use their best judgment, based on the nature and urgency of the clinical situation, and may proceed with unblinding without having successfully reached and discussed the situation with the Sponsor.

If a patient's study drug assignment has been unblinded for a medical emergency, the Sponsor must be notified within 24 hours of the unblinding event. The reason and the date of the unblinding must be documented clearly in the patient's source documents. Information regarding the study drug assignment obtained from the unblinding must be maintained in a secure location with controlled access and must not be shared with the Sponsor, contract research organization, or any site personnel (other than the physician treating the patient). In addition, the Investigator must consider whether the clinical event that prompted unblinding must be considered an SAE, according to the regulatory definitions or criteria for SAEs, and if so, submit an SAE report, per [Section 7.11](#). If a patient's study drug assignment is unblinded for a medical emergency or urgent clinical situation, the patient must discontinue study drug.

The Sponsor or designee may also unblind any SAE reports in compliance with regulatory reporting requirements. In addition, the Sponsor may, for matters relating to safety concerns, unblind individual patients at any time.

5.12. Prior and Concomitant Treatment and Procedures

5.12.1. Prior Medications and Procedures

Information regarding any medication or non-drug therapy or procedure taken or performed within 30 days prior to screening and before the first dose of study drug must be documented in the patient's source documents and the electronic case report form (eCRF).

5.12.2. Prior Anticancer Medications and Procedures

Any prior anticancer medication or procedure must be documented in the patient's source documents and the eCRF.

5.12.3. Concomitant Medications

All medications, including vitamin supplements, over-the-counter medications, and oral herbal preparations; non-drug therapies taken on or after the first day of study drug dose through and including 30 days after the last dose of study drug must be documented in the patient's source documents and the eCRF. In addition, any new treatments taken after the last dose of study drug through 30 days after the last dose must be documented in the patient's source documents and the eCRF.

The date and time of concomitant H2 receptor antagonist and antacid administration must be recorded 3 days prior to the study visit and on the day of the visit in the patient's source documents and the eCRF.

5.12.3.1. Permitted Medication

Patients may receive medications for symptomatic relief (eg, analgesics, laxatives, antiemetics).

Medications that increase gastric pH (eg, antacids), with the exception of proton pump inhibitors, may be taken provided they are not administered within 2 hours before or after administration of study drug.

